## PROTOCOL SYNOPSIS

Protocol Title:	The Effects of Dupilumab on Allergic Contact Dermatitis
Site Numbers & Names:	001 Brigham and Women’s Hospital, Department of Dermatology
Research Hypothesis:	Dupilumab will most likely benefit patients who have persistent allergic contact dermatitis to allergens that primarily elicit a Th2 immune response (ie rubber and fragrance) but may also benefit patients who have sensitivities to allergens that primarily elicit Th1, Th17 and Th22 immune responses (ie nickel).
Study Schema: Drugs / Doses / Length of Treatment)	Dupilumab 300 mg/2mL; 7 doses; 10 weeks of treatment
Study Objectives: 
 
• Primary:
 
• Secondary:
 
	
 
• Primary endpoint 1: Number of patients who achieve a reduction in patch test site reactions from 2+–3+ at baseline to “?” or no reaction at week 12.
 
• Secondary endpoint 1: Number of patients who achieve a reduction in investigator global assessment (IGA; IGA = vIGA-AD) from 3 or greater at screen and baseline to 0 or 1 at Week 6 and at Week 12.
 
• Secondary endpoint 2a: To quantify the inflammatory markers (Th1, Th2, Th17, Th22 immune pathways) in the blood and skin of patients before and after dupilumab. Secondary endpoint 2b: Changes in IGA from baseline to week 12. Other secondary endpoints: Change in baseline eczema-area-and-severity-index (EASI), body surface area (BSA), numerical rating scale (NRS) itch, dermatology life quality index (DLQI), and SLEEPYQ from baseline to Week 6 and Week 12.
 
• Secondary endpoint 3: Changes in IGA from baseline to Week 6 and to Week 12.
 
• Secondary endpoint 4: To identify and quantify the top T cell clones by T-cell receptor high-throughput sequencing in the skin and blood before therapy and quantify their abundance after therapy.
 
• Other secondary endpoints: Change in baseline eczema-area-and-severity- index (EASI), body surface area (BSA), numerical rating scale (NRS) itch, dermatology life quality index (DLQI), and SLEEPYQ from baseline to Week 6 and to 12.
 

Study Design:	
We will recruit 30 patients with allergic contact dermatitis 18 years of age and older up to 18 months after patch testing with a documented IGA of at least 3 at baseline and screening visits, and at least one 2+ (strong) or 3+ (extreme) reaction on patch testing to participate in this open-label pilot study. If more than one 2+ (strong) or 3+ (extreme) reactions are present, up to two may be selected for evaluation in the study. Priority will be given to nickel, fragrance mix I or II, and rubber as these allergens have been studied previously with respect to their preferential T helper cell skewing. At the initial screening visit, demographic information will be obtained, inclusion and exclusion criteria as detailed in Section 4.2 will be reviewed, and informed consent obtained for those deemed eligible for enrollment. A single subcutaneous dose of 600 mg will be self-administered at week 0 +72-120 hours and 300 mg every 2 weeks thereafter for a total 10 weeks of therapy. Subjects will be evaluated for improvement in primary and secondary endpoints using clinical examination and questionnaires during initial and follow-up visits at Week 0, Week 6, and Week 12 as per Time and Events Schedule below. Patch test site reactions will also be evaluated 72 hours after the Week 0 and Week 12 visits. Skin biopsies will be taken at these two time points from both the patch test site reaction and from normal skin taken from a non-dermatitic area on the contralateral side of the body. For the Week 12 patch placement, a site contralateral to the Week 0 patch placement site will be chosen. If an area of persistent dermatitis other than the patch test site(s) is also present at week 12+72-120 hours an additional biopsy will be taken unless in an anatomic location not amenable to biopsy (face, hands, elbows, knees, genitals, feet). Serum samples will be obtained at four time-points including Week 0 (prior to patch placement), Week 0 +72-120 hours, Week 12 (prior to patch placement), and Week 12 +72-120 hours. If subjects do not mount a 2+ (strong) or 3+ extreme reaction to the tested allergens at the Week 0 +72 hour visit they will be discontinued from the study and will not receive dupilumab. These patients will be considered screen fails. Week 10 +72-120 hours will conclude the end of the treatment portion of the study. Week 12 +72-120 hours will conclude the subjects' participation in the study.

Accrual Goal: (Total number of subjects)	30 subjects
Accrual Rate: (Number of subjects expected per month)	1 subject/month
FPFV: LPFV: Follow Up: (dd-mm-yy)	FPFV: 09-01-18; LPFV: 05-01-20; Follow Up: 3 months after FV

Correlative Studies: (PK/PD, etc.)
	

Inclusion Criteria:
	
 
1. At least 18 years of age
 
2. At least one contact allergen with a 2+ (strong) or 3+ (extreme reaction) confirmed by patch testing within 18 months of the baseline visit that can be duplicated at the initiation of the study (placement at Week 0 and patch test reaction read at Week 0 +72-120 hours).
 
3. Allergic contact dermatitis diagnosed clinically by the principle investigators who have expertise in allergic contact dermatitis
 
4. Investigator's global assessment score of at least 3 (range 0-4) at the screening and baseline visits
 
5. Documented recent history (within 18 months of patch testing) of inadequate response to treatment with topical medications and allergen avoidance
 
6. Able and willing to provide informed consent, participate in study visits, and undergo visit procedures.
 

Exclusion Criteria:	

1. Prior dupilumab use

2. Treatment with a systemic immune-regulating medication within 3 months of the baseline visit or the patient's prior patch testing, whichever is longer. Examples of these medications include azathioprine, methotrexate, mycophenolate mofetil, Janus kinase inhibitors, and phototherapy (including tanning booths). Cyclosporine or prednisone may not have been used within 1 month of the baseline visit.

3. Treatment with other biologic agents, such as TNF inhibitors, anti-IL 17 agents, anti-IL 12/23 agents, or anti-IL 23 agents, within 4 months of baseline visit or the patient's prior patch testing, whichever is longer.

4. Use of rituximab within at 6 months (or until lymphocyte counts have normalized if longer than 6 months) of the baseline visit or the patient's prior patch testing, whichever is longer.

5. Treatment with topical corticosteroids, topical phosphodiesterase inhibitors or topical calcineurin inhibitors within 1 week before the baseline visit

6. Other active conditions, such as psoriasis, that may confound clinical evaluations of dermatitis and patient-reported symptoms.

----------------------------	---


Exclusion Criteria (continued)
	
7. Increased risk of infection or reactivated infection, including history of human immunodeficiency virus, hepatitis B, hepatitis C, endoparasitic infections, receipt of a live attenuated vaccine within 3 months of the baseline visit, chronic or acute infection requiring treatment within 4 weeks of the baseline visit, immunosuppressed status (ie recurrent or resistant opportunistic infections)
 
8. Malignancy within 5 years of the screening visit excluding local cutaneous squamous cell carcinoma, basal cell carcinoma or cervical carcinoma in situ that has been fully treated.
 
9. Women who are or plan to become pregnant or breastfeed during study participation or are unable or not willing to use birth control during the study and for 4 months after the last dose of dupilumab. Options for birth control include abstinence, double barrier (ie male condom and female diaphragm), vasectomy, intrauterine device, and hormonal contraception. Females who have not had menses within 1 year of the baseline, bilateral tubal ligation, hysterectomy, and/or bilateral oophorectomy visit do not require additional methods contraception during study participation.
 
10. Unstable condition or status, as per study investigator's judgment, that may lead to more likely discontinuation from the study including but not limited to major, recurrent medical illnesses that may require hospital admission and/or discontinuation of dupilumab, surgery that would require discontinuation of dupilumab and/or major rehabilitation, inability to participate in all study visits and administer dupilumab.
 
11. Resident outside of Massachusetts, Connecticut, Rhode Island, New Hampshire, Maine or Vermont state.
 
12. Unable to use Zoom videoconferencing.

Criteria for Evaluation: (Efficacy, safety, stopping rules, etc.)
	

Statistics:
	

# 1 INTRODUCTION

## 1.1 Background on Allergic Contact Dermatitis

Allergic contact dermatitis (ACD) is a chronic, inflammatory dermatitis affecting millions of Americans yearly and has significant negative impacts on patient quality of life and the economy. Contact dermatitis has an estimated prevalence rate of 13.6 cases per 1000 population, with 8.4 million office visits, 4 million workdays, and \$400 million lost yearly in the United States. Identification of allergens through patch testing and subsequent avoidance is the first-line treatment along with topical corticosteroids. However, in certain patients, such as those with implantable devices or occupational exposures, allergen avoidance is difficult or impossible and represents a major unmet clinical need. Dupilumab is a promising treatment for allergic contact dermatitis through its blockade of the cytokines IL-4 and IL-13 that are central in the differentiation and maintenance of Th2 cells and its ability to also normalize Th1, Th17, and Th22-mediated immune pathways. Blockade of this pathway in ACD patients and the study of their skin and blood before and after treatment offers a unique opportunity to improve our understanding of disease mechanisms in human ACD and the potential role for dupilumab in addressing this unmet need.

## 1.2 Role of T cells in Allergic Contact Dermatitis and Dupilumab

Current treatment strategies for ACD include allergen avoidance and the use of topical or systemic immunosuppressive agents. However, for many patients allergen avoidance can negatively affect quality of life or be inadequate, particularly in cases of unavoidable occupational exposures or implanted devices. While allergic contact dermatitis was originally posited to be a Th1-predominant disease, the important roles played by Th2, Th17 and Th22 cells is increasingly recognized. Activation of inflammatory pathways in ACD can be allergen specific, with differential upregulation of innate immune, Th1, Th2, Th17, and/or Th22 signaling. Specifically, nickel induces a strong Th1, Th17 and Th22 response, while fragrance and rubber have preferential TH2 stimulation. This is in contrast to atopic dermatitis, a predominantly Th2-mediated inflammatory reaction driven by the cytokines IL-4, IL-5 and IL-13. In atopic dermatitis, the cytokines IL-4 and IL-13 are the main pathogenic cytokines. These instructive cytokines both induce activated naïve T cells to become Th2 cells and maintain the survival of Th2-derived memory T cells. These cytokines can also alter chemokine expression and trafficking to inflamed tissue. The IL-4 and IL-13 receptors share the common subunit IL-4R $\alpha$ . Dupilumab, an inhibitor of IL-4R $\alpha$ , is FDA-approved for the treatment of atopic dermatitis. Despite its specific targeting of Th2-mediated pathology, it has also been shown to normalize Th1-,

and Th17-related gene expression in the skin of patients with atopic dermatitis. Therefore, we hypothesize that dupilumab will most likely benefit patients who have persistent allergic contact dermatitis to allergens that primarily elicit a Th2 immune response (ie rubber and fragrance), but may also benefit patients who have sensitivities to allergens that primarily elicit Th1, Th17, and Th22 immune responses (ie nickel). We propose to test this hypothesis by treating patients who have failed allergen avoidance and skin directed therapy with dupilumab and monitoring their responses in the following ways before and after therapy: using well-established clinical parameters addressing skin inflammation and quality of life issues, assessing whether the most abundant T cell clones (defined as the top 5 most abundant clones present in the skin at patch test site before therapy) can still traffic to the skin after therapy, and quantifying the changes in the inflammatory Th1, Th2, Th17 and Th22-specific immune gene signatures before and after treatment.

## **1.3 Summary of Results of Investigational Program**

### **1.3.1 Pharmacology of Dupilumab**

Dupilumab is a human monoclonal IgG4 antibody that inhibits interleukin-4 (IL-4) and interleukin-13 (IL-13) signaling by specifically binding to the IL-4R $\alpha$  subunit shared by the IL-4 and IL-13 receptor complexes. Dupilumab inhibits IL-4 signaling via the Type I receptor and both IL-4 and IL-13 signaling through the Type II receptor.

Blocking IL-4R $\alpha$  with dupilumab inhibits IL-4 and IL-13 cytokine-induced responses, including the release of proinflammatory cytokines, chemokines and IgE.

### **1.3.2 Human Pharmacokinetics of Dupilumab**

#### **Absorption**

Following an initial subcutaneous (SC) dose of 600 mg, dupilumab reached peak mean  $\pm$ SD concentrations (Cmax) of 70.1 $\pm$ 24.1 mcg/mL by approximately 1 week post dose.

Steady-state concentrations were achieved by Week 16 following the administration of 600 mg starting dose and 300 mg dose either weekly (twice the recommended dosing frequency) or every other week. Across clinical trials, the mean  $\pm$ SD steady-state trough concentrations ranged from 73.3 $\pm$ 40.0 mcg/mL to 79.9 $\pm$ 41.4 mcg/mL for 300 mg administered every 2 weeks and from 173 $\pm$ 75.9 mcg/mL to 193 $\pm$ 77.0 mcg/mL for 300 mg administered weekly. The bioavailability of dupilumab following a SC dose is estimated to be 64%. Distribution The estimated total volume of distribution was approximately 4.8 $\pm$ 1.3 L.

**Elimination** The metabolic pathway of dupilumab has not been characterized. As a human monoclonal IgG4 antibody, dupilumab is expected to be degraded into small peptides and amino acids via catabolic pathways in the same manner as endogenous IgG. After the last steady-state dose of 300 mg Q2W or 300 mg QW dupilumab, the median times to non-detectable concentration (<78 ng/mL) are 10 and 13 weeks, respectively.

**Dose Linearity** Dupilumab exhibited nonlinear target-mediated pharmacokinetics with exposures increasing in a greater than dose-proportional manner. The systemic exposure increased by 30-fold when the dose increased 8-fold following a single dose of dupilumab from 75 mg to 600 mg (i.e., 0.25times to 2-times the recommended dose). **Weight** Dupilumab trough concentrations were lower in subjects with higher body weight. **Immunogenicity** Development of antibodies to dupilumab was associated with lower serum dupilumab concentrations. A few subjects who had high antibody titers also had no detectable serum dupilumab concentrations.

### Specific Populations

#### Geriatric Patients

In subjects who are 65 years and older, the mean  $\pm$ SD steady-state trough concentrations of dupilumab were 69.4 $\pm$ 31.4 mcg/mL and 166 $\pm$ 62.3 mcg/mL, respectively, for 300 mg administered every 2 weeks and weekly. No dose adjustment in this population is recommended.

#### Renal or Hepatic Impairment

No formal trial of the effect of hepatic or renal impairment on the pharmacokinetics of dupilumab was conducted.

#### Drug Interaction Studies

Drug interaction studies have not been conducted with DUPIXENT.

### **1.3.3 Clinical Safety with Dupilumab SC Formulation**

#### **1.3.3.1 Drug-Related Adverse Events**

##### Conjunctivitis

During the 52-week treatment period of concomitant therapy trial (Trial 3), conjunctivitis was reported in 16% of the DUPIXENT 300 mg Q2W + TCS group (20 per 100 subject-years) and in 9% of the placebo + TCS group (10 per 100 subject-years) [see Warnings and Precautions (5.2)].

##### Eczema Herpeticum and Herpes Zoster

The rate of eczema herpeticum was similar in the placebo and DUPIXENT groups.

Herpes zoster was reported in <0.1% of the DUPIXENT groups (<1 per 100 subject-years) and in <1% of the placebo group (1 per 100 subject-years) in the 16-week monotherapy trials. In the 52-week DUPIXENT + TCS trial, herpes zoster was reported in 1% of the DUPIXENT + TCS group (1 per 100 subject-years) and 2% of the placebo + TCS group (2 per 100 subject-years).

#### Hypersensitivity Reactions

Hypersensitivity reactions were reported in <1% of DUPIXENT-treated subjects. These included serum sickness reaction, serum sickness-like reaction, and generalized urticaria [see Contraindications (4), Warnings and Precautions (5.1), and Adverse Reactions (6.2)].

#### Eosinophils

DUPIXENT-treated subjects had a greater mean initial increase from baseline in eosinophil count compared to subjects treated with placebo in the monotherapy trials. Eosinophil counts declined to near baseline levels by Week 16. The initial increase in eosinophils was not observed in the 52-week DUPIXENT + TCS trial.

In Trials 1, 2, and 3, the incidence of treatment-emergent eosinophilia ( $\geq 500$  cells/mcL) was similar in DUPIXENT and placebo groups. In Trials 1, 2, and 3, treatment-emergent eosinophilia ( $\geq 5,000$  cells/mcL) was reported in <1% of DUPIXENT-treated patients and none in placebo-treated patients. In most cases, eosinophil counts declined to near baseline during study treatment.

## **1.4 Research Hypothesis**

Dupilumab will most likely benefit patients who have persistent allergic contact dermatitis to allergens that primarily elicit a Th2 immune response (ie rubber and fragrance) but may also benefit patients who have sensitivities to allergens that primarily elicit Th1, Th17 and Th22 immune responses (ie nickel).

## **1.5 Study Rationale**

One of the most innovative aspects of this proposal is the proposed combination of clinical and translational science to address a potential new cohort of patients that may benefit from the use of dupilumab. By ascertaining the efficacy of dupilumab in a cohort of patients using a combination of robust, well-characterized, clinical scoring and state-of-the-art technologies to identify and quantify changes in T cell trafficking and inflammatory gene and protein signatures, we will determine the extent to which dupilumab dampens the T-cell

response to allergens. Not only are these studies novel in this disease, blockade of IL-4 and IL-13 will lead to a better understanding of allergen-specific disease pathogenesis.

## **2 STUDY OBJECTIVES**

### **2.1 Primary Objective**

To measure the degree to which 2+(strong)-3+(extreme) patch test site reactions are reduced by dupilumab. Based on the International Contact Dermatitis Research Group scoring system (? as a doubtful reaction, + as a mild reaction, possible erythema, infiltration, and papules, ++ as a strong reaction, erythema, infiltration, papules and vesicles, +++ as a very strong reaction, intense erythema, infiltration, and coalescing vesicles, IR as an irritant reaction), we will measure patch test site reactions at two time points, both prior to starting dupilumab (Week 0 +72-120 hours) and 12 weeks after starting dupilumab.

### **2.2 Secondary Objectives**

Secondary endpoint 1: Number of patients who achieve a reduction in investigator global assessment (IGA) from 3 or greater at screen and baseline to 0 or 1 at Week 6 and Week 12.

Secondary endpoint 2a: To quantify the inflammatory markers (Th1, Th2, Th17, Th22 immune pathways) in the blood and skin of patients before and after dupilumab. Using novel nanostring-based gene expression assays and multispectral immunofluorescence we will quantify changes in key genes that are specific for the Th1, Th2, Th17, Th22 immune pathways in the skin and blood of patients before and after treatment with dupilumab. Secondary endpoint 2b: Changes in IGA from baseline to week 12. Other secondary endpoints: Change in baseline eczema-area-and-severity-index (EASI), body surface area (BSA), numerical rating scale (NRS) itch, dermatology life quality index (DLQI), and SLEEPYQ from baseline to Week 6 and Week 12.

Secondary endpoint 3: To measure the reductions in the severity of clinical skin disease and quality of life scores with dupilumab treatment. We will measure changes in investigator global assessment (IGA; scored on a scale of 0-5 with 0 being no disease and 5 being the most severe disease) from baseline to Week 6 and Week 12.

Secondary endpoint 4: To address whether dupilumab affects T cell trafficking, use high-throughput sequencing of the T-cell receptor (TCR HTS) to identify the unique

CDR3 sequence of the likely pathogenic T cell clones before therapy and quantify their relative frequency in the skin after dupilumab therapy.

### **3 ETHICAL CONSIDERATIONS**

#### **3.1 Good Clinical Practice**

This study will be conducted in accordance with Good Clinical Practice (GCP), as defined by the International Conference on Harmonization (ICH) and in accordance with the ethical principles underlying the United States Code of Federal Regulations, Title 21, Part 50 (21CFR50). Study procedures and guidelines are outlined in this protocol and any changes to the protocol or informed consent forms will be submitted for IRB approval prior to their use. Any serious breaches in GCP, such as those leading to risks to patients or study validity, will be reported to Regeneron. All team members involved in the study will have appropriate qualifications to complete their responsibilities. Anyone with a history of scientific misconduct or fraud or anyone against whom sanctions have been invoked will not participate in the study.

#### **3.2 Institutional Review Board/Independent Ethics Committee**

The IRB will review and approve all study materials including the protocol, informed consent form, and any other written information provided to subjects. A copy of the Investigator Brochure or product labeling information provided to subjects should be given to the IRB. Other information required by institutional procedures or regulatory agencies should also be given to the IRB.

#### **3.3 Informed Consent**

Informed consent requires that patients are clearly and fully informed about the purpose, risks, and any other important information related to the study in which they are agreeing to participate. The rights, safety, and well-being of individual patients take precedence over other considerations including those of scientific investigation and society.

Investigators must provide a copy of the informed consent form, signed and dated by the subject and the investigator who conducted the discussion of informed consent. The informed consent form should be written in lay language that is easy to understand and must be approved by the IRB prior to its use. All revisions to the informed consent form, which should be done when new, pertinent information

related to subject consent arises, also require IRB approval. All subjects participating in the study should be notified of the changes to the informed consent form and discuss with the investigator whether they plan to continue in the study. During the informed consent process, adequate time must be given to subjects so that they may review and ask questions about the study. The investigator should document all discussions regarding informed consent.

## **4 INVESTIGATIONAL PLAN**

### **4.1 Study Design and Duration**

Patients previously seen at the Contact Dermatitis and Occupational Dermatology Program at Brigham and Women's Hospital that meet the inclusion criteria will be recruited. In addition, patients will be invited to participate in the study directly during their clinical visit. Patients may be identified and provided information about the study at the time of their patch testing visits and/or follow-up appointments. Additionally, patients who have been patch tested that inform us they are not improving following the allergen avoidance recommendations may also be provided information about the study.

A cover letter describing the study, signed by PI will be sent to the subjects at least a week in advance of their scheduled study visit with the PI or Co-Investigator. In addition, an informed consent document will be sent with the letter to them to read over and discuss with family and others (including their healthcare providers). If interested in participating in the study, the subject will be asked to bring the informed consent document to the visit with the PI or Co-Investigator.

Patients identified directly during the office visit will be approached by a study staff other than PI. They will be provided with a cover letter and the informed consent document to take home and read and discuss with family members. Subsequent follow-up may include contact via mail, post or phone calls to patients to provide additional information about the study. Patients who read the consent form at the clinic and feel comfortable enough to consent to participate in the study, may be enrolled right away.

It will be emphasized that participation is purely voluntary and will not influence the care or ability to get care within our institution any provider.

In person study visits will take place at the clinical rooms of the Center for Clinical Investigations (CCI), the Ambulatory Clinical Center at [name]. In

addition, virtual study visits will take place using Healthcare Secure Zoom. Prior to their scheduled study visits, a research assistant will prepare the administrative paperwork informed consent, information materials, prospective visit schedule and the physician questionnaires.

We will recruit 30 patients with allergic contact dermatitis 18 years of age and older up to 6 months after patch testing with a documented IGA of at least 3 at baseline and screening visits, and at least one 2+ (strong) or 3+ (extreme) reaction on patch testing to participate in this open-label pilot study. If more than one 2+ (strong) or 3+ (extreme) reactions are present, up to two may be selected for evaluation in the study. Priority will be given to nickel, fragrance mix I or II, and rubber as these allergens have been studied previously with respect to their preferential T helper cell skewing. At the initial screening visit, demographic information will be obtained, inclusion and exclusion criteria as detailed in Section 4.2 will be reviewed, and informed consent obtained for those deemed eligible for enrollment. A single subcutaneous dose of 600 mg will be self-administered at week 0 +72-120 hours and 300 mg every 2 weeks thereafter for a total 10 weeks of therapy. Subjects will be evaluated for improvement in primary and secondary endpoints using clinical examination and questionnaires during initial and follow-up visits at Week 0, Week 6, and Week 12 as per Time and Events Schedule. Patch test site reactions will also be evaluated 72 hours after the Week 0 and Week 12 visits. Skin biopsies will be taken at these two time points from both the patch test site reaction and from normal skin taken from a non-dermatitic area on the contralateral side of the body. For the Week 12 patch placement, a site contralateral to the Week 0 patch placement site will be chosen. If an area of persistent dermatitis other than the patch test site(s) is also present at week 12+72-120 hours an additional biopsy will be taken unless in an anatomic location not amenable to biopsy (face, hands, elbows, knees, genitals, feet). Serum samples will be obtained at four time-points including Week 0 (prior to patch placement), Week 0 +72-120 hours, Week 12 (prior to patch placement), and Week 12 +72-120 hours. If subjects do not mount a 2+ (strong) or 3+ extreme reaction to the tested allergens at the Week 0 +72-120 hour visit they will be discontinued from the study and will not receive dupilumab. These patients will be considered screen fails. Week 10 +72-120 hours will conclude the end of the treatment portion of the study. Week 12 +72-120 hours will conclude the subjects' participation in the study.

We developed a contingency plan in case there is a resurgence of COVID, a pandemic, closure of facilities or other act of God that prevents the study visit schedule to be completed in person. In such case, we will add a virtual visit component to our in-person visits to complete some of the research activities related to that visit.

Please see the Time and Events Schedule for full details.

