### **4.2.1 Inclusion Criteria**

The following inclusion criteria are required for patient participation in the study:

1. At least 18 years of age
2. At least one contact allergen with a 2+ (strong) or 3+ (extreme reaction) confirmed by patch testing within 18 months of the baseline visit that can be duplicated at the initiation of the study (placement at Week 0 and patch test reaction read at Week 0 +72-120 hours).
3. Allergic contact dermatitis diagnosed clinically by the principle investigators who have expertise in allergic contact dermatitis
4. Investigator's global assessment score of at least 3 (range 0-4) at the screening and baseline visits
5. Documented recent history (within 18 months of patch testing) of inadequate response to treatment with topical medications and allergen avoidance
6. Able and willing to provide informed consent, participate in study visits, and undergo visit procedures.

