## **6.4 Efficacy Assessments**

### **6.4.1 Primary Efficacy Assessment**

The following clinical assessments will provide outcome data:

Number of patients who achieve a reduction in patch test site reactions from 2+-3+ at baseline to "?" or no reaction at week 12 +72-120 hours.

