#### **6.4.2.2 Secondary Non-Clinical Endpoints**

Serum samples will be collected at baseline and week 12 prior to patch placement for analysis of inflammatory cells and markers. Additionally skin and serum

samples will be collected for analysis of inflammatory cells and markers 72 hours after patch placement at baseline and week 12. We will also collect one additional biopsy from an area of persistent, chronic dermatitis if present after the 10-week course of dupilumab. Skin biopsies will be collected at 72 hours after patch testing from the sites of allergen placement and will be initially placed in saline. Blood samples will also be collected on the same day. DNA and RNA will be isolated from PBMCs and 300 um of tissue. The isolated DNA will be subjected to TCR HTS of the TCRB gene before and after therapy. We will determine the CDR3 sequence of the top 5 most prevalent clones in the skin of patch tested skin before therapy, which likely represents at least one of the pathogenic T cell clones specific to the allergen. We will quantify the presence and abundance of those same clones in the blood and patch tested skin after therapy as a measure of T cell trafficking (ie ability of those same T cell clones being able to reenter skin at site of specific allergen placement may be inhibited after dupilumab therapy). The RNA will be subjected to multiplex gene expression analysis of 594 human immune genes to specifically characterize the Th1, Th2, Th17, and Th22 skewing of the immune microenvironment as well as quantify the expression of alarmins and proteases known to be important in the elicitation phase of allergic contact dermatitis. These gene signatures and immune cell subtypes analyses will be confirmed at the protein level with multispectral immunofluorescence on the skin and flow cytometry in the blood.

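### The placement-to-reading interval for the primary patch test is stated inconsistently and never matched within patient, so a patient's Week 0 and Week 12 readings may differ by up to 48 hours

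*Combined protocol and SAP*

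**What the plan says.** All references are to the combined protocol and SAP. The interval from patch placement to reading appears in three forms.

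- **72 hours.** The synopsis and 4.1 share the sentence "Patch test site reactions will also be evaluated 72 hours after the Week 0 and Week 12 visits". Section 6.4.2.2 uses the same figure for tissue: "Skin biopsies will be collected at 72 hours after patch testing from the sites of allergen placement".
- **72-120 hours.** Inclusion criterion 2 in 4.2.1 has "placement at Week 0 and patch test reaction read at Week 0 +72-120 hours". The primary objective in 2.1 gives the range for baseline only: "both prior to starting dupilumab (Week 0 +72-120 hours) and 12 weeks after starting dupilumab". The endpoint in 6.4.1 has "no reaction at week 12 +72-120 hours", and 9.4.3 repeats it. The headings of Visits 3 and 6 in the 6.1 schedule carry the same range.
- **Day 4 and Day 87.** The 6.1 schedule places the two reading visits on these days, in a row labelled +/- 3 days that also covers the placement visits on Days 1 and 84.

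The reading that decides whether a patient stays in the study differs between two otherwise matching paragraphs. The synopsis has "reaction to the tested allergens at the Week 0 +72 hour visit they will be discontinued from the study"; section 4.1 has "reaction to the tested allergens at the Week 0 +72-120 hour visit they will be discontinued from the study".

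The study is open-label with a single group. I found no statement of which timing governs, no requirement that a patient's two intervals be equal, and no provision to record elapsed hours or use them in the analysis.

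**The concern.** The primary endpoint counts patients whose reaction falls from 2+ or 3+ to doubtful or none. It rests on two readings per patient, so anything that differs between them apart from treatment can enter the result. Time since placement is one such factor if the grade of a reaction depends on it. The plan leaves that time loose, and no control group is read on the same schedule to show what timing alone would do.

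Entry makes this sharper. A patient receives dupilumab only if the Week 0 reading is 2+ or 3+, so the first reading is selected for being high and the second is not. If grade varies with elapsed time, selection favours patients who were read when their reaction was strong, and an unmatched Week 12 reading would then tend to be lower without any drug effect.

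The gene-expression and T-cell clone comparisons use biopsies and blood from the same visits, so they inherit any mismatch.

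**Working it through.** **1. Figures in the plan that bear on this.** The plan puts no figure on the effect of reading time. Its sample size (11, raised to 14) does not depend on it, and it reproduces: a paired t-test with mean change 1.0 and SD 1.0 needs 10 patients for 80% power; 10 / (3/π) = 10.47, which rounds up to 11. Simulated power of the exact signed-rank test at n = 11 is 80.9%. Nothing below changes that number.

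**2. Nominal interval in the schedule (6.1).** Day 4 - Day 1 = 3 days = 72 h. Day 87 - Day 84 = 3 days = 72 h. The nominal days therefore agree with the 72-hour text and with the lower end of 72-120 hours.

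**3. Can the +/- 3 days apply to the placement-reading pairs?** Taken literally, Visit 5 falls on Days 81-87 and Visit 6 on Days 84-90. The earliest gap is 84 - 87 = -3 days, a reading before the patch is placed. The label therefore cannot be meant as printed for these visits, but the table does not exempt them.

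**4. Permitted difference between one patient's two readings.**

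| Rule | Shortest interval | Longest interval | Largest within-patient difference |
|---|---|---|---|
| 72 h exactly | 72 h | 72 h | 0 h |
| 72-120 h | 72 h | 120 h | 120 - 72 = 48 h, in either direction |

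**5. What 48 hours might mean in practice (assumption).** If both readings fell independently and uniformly within 72-120 h, the mean absolute difference would be 48 / 3 = 16 h. The share of patients differing by 24 h or more would be (1 - 24/48)² = 25%. The documents do not say how visits will be booked, so this is only an illustration.

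**6. From hours to grade.** This step cannot be taken from the documents, because no section says how a reaction changes between 72 and 120 hours. Timing differences unrelated to the visit would mostly add noise. Bias needs either a systematic difference between Week 0 and Week 12 or the selection mechanism described above, and both require that grade depends on elapsed time in this range.

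**The case against.** The case for leaving the text alone has real strength. The sections that define entry and the endpoint (4.2.1, 6.4.1, 9.4.3), the baseline reading in 2.1 and the Visit 3 and 6 headings all use 72-120 hours. A bare 72 hours lies inside that range and equals the nominal gap between visit days, so a reader can work out the likely operative window. A specific column heading would also normally override a general row label. All of this stands: 72 hours against 72-120 hours is loose drafting, not a contradiction.

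One could add that 2.1 sets the second reading 12 weeks after the first dose, which would match the intervals if the two placements were exactly 12 weeks apart. But the Week 12 visit has its own window, and 6.4.1 allows the full range.

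Two stronger readings are tempting and are not supported.

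- A reader might infer from the +/- 3 days that readings could fall 0 to 144 hours after placement, or 3 days before to 9 days after it. Those figures need the row label to override the headings in the same table, and they lead to the impossible case in step 3. They show that a footnote is missing; they do not measure the problem.
- A reader might infer a number of false responders. That needs a rate of spontaneous fading that the documents do not give, and an early-then-late shift in every patient. The endpoint is also demanding: a 2+ or 3+ reaction must pass below 1+ to count.

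What the objection does not remove is the 48 hours that remain under the reading most favourable to the plan.

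**Conclusion.** The point holds as a drafting inconsistency together with a missing rule. The interval needs to be reconciled, the screen-fail reading differs between the synopsis and 4.1, and the +/- 3 day label needs an exemption. Independently of these, a patient's two readings and biopsies may differ by up to 48 hours in elapsed time with nothing requiring a match. In an uncontrolled before/after comparison that selects on a high first reading, this can add noise and possibly bias. That rests on the assumption that grade varies with time between 72 and 120 hours; the documents establish neither the size nor the direction. The sample size is unaffected. This is an inexpensive improvement to make before data are collected, and not grounds to call the primary comparison invalid.

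**What to change.** - State one placement-to-reading interval in the synopsis, 2.1, 4.1, 4.2.1, 6.1, 6.4.1, 6.4.2.2 and 9.4.3, and use it for the screen-fail reading as well. Changing only some of these sections would create new mismatches.
- Add a note to the 6.1 schedule that the +/- 3 days does not apply to Visits 3 and 6, which are timed from the actual placement.
- Require the Week 12 reading and biopsy at the same elapsed time as that patient's Week 0 reading and biopsy, within a tolerance that the sponsor sets.
- Record elapsed hours at both readings. If they are not captured at the visit, they may not be recoverable.
- Report the primary result again by interval difference, as a sensitivity analysis.

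Visit 3 is also the first-dose visit, so the dosing passages (synopsis, 4.1, 5.1, 5.3) must be kept consistent with whichever interval is retained.

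The cost is protocol wording and slightly tighter booking, with no added visit. The sensitivity analysis will be imprecise: at the minimum of 14 completers, one patient is 1/14 = 7.1 percentage points of the responder proportion. Matching the intervals at the visits therefore matters more than adjusting for them afterwards.
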